5. SUMMARY OF REGISTRY DESIGN

PLOTS is a multicenter, post-approval study of the SPiN System™ in percutaneous localization. It's an open-label registry study practically focused on the expedient intraoperative localization and removal of small pulmonary nodules in subjects undergoing lung nodule resection. The study will aim to collect data from 70-100 patients at approximately 5 thoracic surgery sites distributed across the U.S. Each site is expected to enroll a minimum of 6 subjects. Enrollment will be monitored and will stop once sufficient data has been collected.

All post-surgical treatment decisions and clinical assessments will be at the discretion of the patient's cardiothoracic surgeon or clinician per usual care, not be mandated by registry design. Please refer to Table 2 for a diagram of the [study flow](#).

6. DEVICE DESCRIPTION

Definition of medical device: under 21 U.S.C. 321(h), a medical device is an instrument, apparatus, implement, machine, contrivance, implant, in vitro reagent, or other similar or related article, including any component, part, or accessory, which is:

- recognized in the official National Formulary, or the United States Pharmacopeia, or any supplement to them,
- intended for use in the diagnosis of disease or other conditions, or in the cure, mitigation, treatment, or prevention of disease, in man or other animals, or
- intended to affect the structure or any function of the body of man or other animals, and which does not achieve its primary intended purposes through chemical action within or on the body of man or other animals and which is not dependent upon being metabolized for the achievement of its primary intended purposes.

The SPiN System is designed to help guide the physician with electromagnetic navigation while using a bronchoscope to help visualize nodules, and a transthoracic needle to reach nodules in a single procedure setting. Veran System components include an electromagnetic field generator, a locatable sensor probe that allows navigation through the bronchi/chest wall and computer software that creates virtual images for procedural guidance.

In this study, the Veran System and sampling instruments will be used according to the associated Instructions for Use (IFU) (Appendix A) and in accordance with approved product labeling. The SPiN System utilized in this study will have SPiN Drive and SPiN Planning software version 4.0 or higher. Minor software updates are allowed if performed at all study sites within a reasonable timeframe. Under this circumstance, appropriate Investigator/site training must follow a software update and must also be noted in each investigator's study binder.

6.1 Materials Used

Veran Medical Technologies manufactured medical devices used in this study are SPiN Thoracic Navigation System™ with an assortment of needles having guidewires, SPiN Perc™ kit, and introducer and localization needles.

Table 6.1	
Device Name	SPiN Thoracic Navigation System™ and tools
Type	Medical Device
Device Level	II
Status	Approved Medical Device
Procedural Registry	Refinement of localization technique
Sourcing	Veran Medical Technologies
Current/Former Name(s) or Alias(es)	Veran Medical Technologies Aliases

1. The Veran SPiN Thoracic Navigation System™ and SPiN Perc™ Kit were cleared to market by the U.S. Food and Drug Agency (FDA) under 510(k) (K170023).
2. 510(K) Number K122106 Device Name. SPIN DRIVE ALWAYS-ON TIP TRACKED STEERABLE CATHETER ALWAYS-ON TIP TRACKED SHEATH ALWAYS-ON TIP TRACKED ASPIRATION NEEDLE.
3. Please find the instructions for use and the package labeling in Appendix A.
4. Transthoracic training and usage of the needles and System were covered in didactic, peer-to-peer, site initiation visit, and cadaver course trainings.

AOTT Localization Needles (Thoracic)

INS 5610 SPiN Perc™ Localization Needle 19 gu x 105mm with 1cm marking zone.
INS 5611 SPiN Perc™ Localization Needle 10 gu x 105mm with 2cm marking zone.

SPiN Perc™ Kits

INS-5600 SPiNPerc™ Biopsy Needle Guide Kit (Includes INS 5029).
INS 5620 SPiNPerc™ Biospy Needle Guide Kit (20 cm).

SPiN System and Components

SYS-0185 SPiN Planning Laptop.
SYS-1500 SPiN View System.
SYS-3000 IG4 System.
SYS-4000 SPiN Thoracic Navigation System 120 volts 60 hz (US).

6.2 Other Medical Devices

Devices (not manufactured by or for Veran Medical Technologies) used in this study are expected to include 1cc – 3cc Luer lock syringes, Olympus MP-160 or BF-190 bronchoscope, and microcoils and fiducials.

6.3 Instructions for Use

Instructions for use of the medical device are provided (Appendix A). All device deficiencies (including malfunction, use error and inadequate labeling) shall be documented and reported by the investigator throughout the clinical investigation, following the instructions and form found in section Appendix C.

7. PRIOR CLINICAL DATA

Current recommendations from the American College of Chest Physicians (ACCP) evidence-based guidelines for the management of pulmonary nodules begin with examination of the nodule, and an estimation of the clinical probability that the nodule is malignant and evaluation of surgical risk. For subjects with a high probability of cancer (>60%), diagnosis by biopsy and resection are recommended. More than 40% of lung targets are not accessible by conventional bronchoscopy due to their location, with contributing factors including the small diameter of the airways, lack of an airway leading to a nodule and maneuverability difficulties (Rivera et al, 2003; Alberts and Colice, 2003).

The ability to identify and to obtain diagnostic tissue from PPNs has been evaluated in various clinical trials using a variety of techniques. The results over time are variable and do warrant further investigation. Techniques such as diagnostic bronchoscopy alone, and then in comparison with EMN-guided bronchoscopy, EMN-TTNA, and r-EBUS were studied in the large, multicenter registry-based clinical effectiveness study (AQuIRE Registry) (*ibid.*). The AQuIRE registry had a primary objective to measure and identify the determinants of diagnostic yield for bronchoscopy in patients with peripheral lung lesions. Secondary outcomes included diagnostic yield of different sampling techniques, complications, and practice pattern variations. Subjects were enrolled at 15 centers having 22 study physicians between 2009-2014, and the registry was funded by the CHEST organization.

Ost *et al.* reported unexpectedly low diagnostic yields for electromagnetic navigation.

Regarding the low EMN rate, one AQuIRE PI noted (Semaan R.W., 2016):

“...more than 98% of the EMN cases were performed with a single system (Medtronic, Minneapolis, MN) that lacks additional capabilities, including TTNA under EMN guidance. Since the completion of enrollment in the AQuIRE study, newer EMN technologies have been developed and now allow for a navigational transthoracic approach.”

Ost replied in response that: “In such a scenario, the real question is not whether sensitivity will improve but, rather, by how much sensitivity will improve, and whether that improvement is worth the attendant increase in risk.”

Acknowledging the Hopkins observation that that SD was used in almost all EMN cases, Ost writes:

“They point out correctly that 98% of the cases in the AQuIRE registry were performed with SuperDimension (Medtronic, Minneapolis, MN). I concur that not all EMN systems are the same. There are substantive differences in the imaging and algorithms used between these two systems. Veran uses both inspiratory and expiratory films, whereas SuperDimension does not. Respiratory motion can affect nodule location significantly (2). The data in the AQuIRE registry do not provide insight into how Veran might perform in terms of bronchoscopic yield. On the basis of the difference between EMN systems, I agree that separate studies for the Veran system are warranted. “

As these (AQuIRE) were percutaneous cases using early EMN-guidance, the results of this registry may likewise provide insight into impacts of technological advances. The AQuIRE registry had a primary objective to measure and identify the determinants of diagnostic yield for bronchoscopy in patients with peripheral lung lesions. Secondary outcomes included diagnostic yield of different sampling techniques, complications, and practice pattern variations.

- The AQuIRE registry reported poor diagnostic yields for multiple modalities
 - Bronchoscopic alone: 53.7%
 - r-EBUS when used alone: 57%
 - EMN Yield when used alone was 38.5% (98% of cases were SuperDimension technology)

Of these, 312 subjects in the trial underwent transbronchial biopsy. Using bronchoscopy alone, the diagnostic yield was reported as 63.7%. In earlier work, the average diagnostic yield for peripheral lung lesion biopsy performed with conventional flexible bronchoscopy was reported to be 69% for peripheral lesions greater than 20 mm and 33% for peripheral lesions less than 20 mm, (Mazzone *et al*, 2002; Riveria *et al*, 2003; Schrieber and McCrory, 2003).

Results from studies involving procedural guidance technologies such as electromagnetic navigation (EMN) and radial endobronchial ultrasound (radial EBUS) have also been reported (Ost *et al.*, 2016). Diagnostic yield was reported at 57% with r-EBUS alone, 47.1% with EMN combined with r-EBUS. In another recent study published in the New England Journal of Medicine, a total of 639 subjects underwent bronchoscopy for suspected lung cancer and of those bronchoscopic examinations, 43% were nondiagnostic, including in 25% (120 of 487 subjects) in whom lung cancer was ultimately diagnosed (Silvestri *et al*, 2014). As a result of published yields showing an unacceptable yield for peripheral bronchoscopy, ACCP guidelines recommends that nodules without a CT-bronchus sign should be pursued with EMB-TTNA (Rivera *et al*, 2013).

A prospective, single center pilot study evaluated the safety, feasibility, and diagnostic yield of staged approached for taking biopsy samples in a single procedure setting (Yarmus LB et al., 2016). In this study, enrolled subjects (n=24) underwent EBUS for lymph node staging, followed by EMN-bronchoscopy, and EMN-TTNA. The researchers report a diagnostic yield of 83% for EMN-TTNA alone, and 87% when combined with EMN-bronchoscopy. The diagnostic yield increased to 92% when combined with EBUS. There were five (21%) pneumothoraces of which two (8%) required chest tube placement. No bleeding events were observed. The researchers conclude that the results demonstrate an acceptable safety and feasibility profile.

8. RISKS AND BENEFITS

PLOTS is a registry documenting small lung nodule localization techniques used by thoracic surgeons for patients just prior to lung resection. The localization PPNs with dye injection and/or microcoils is a standard medical procedure physicians complete prior to the resection procedure. All procedures represent the clinical standard of care provided by thoracic surgeons to their patients. The following section documents the risks and benefits of Registry participation, as well as the published clinical rates of complications as they are known.

The risks associated with the localization procedure are noted, as well as the use of the device. If approved devices will be used as part of the research, each site may be asked to confirm that the device(s) they are using are being used within their approved labeling

The SPiN Thoracic Navigation System™ and its accessories are marketed for use as tools in the diagnosis and treatment of lung cancer. All devices used in this study are commercially available and there are no anticipated risks beyond those already associated with early lung cancer diagnosis and surgical treatment procedures in clinical practice.

Data, including safety data, will be collected from each subject's nodule localization procedure. The surgical procedure is not experimental in this 510(k)-marketed device that is being used within its approved labeling. Safety data will be summarized and reported from the localization procedure.

8.1 Registry Data Collection – Risks and Benefits

Registry Risks: Every effort will be made to protect the privacy of research subjects. Subject names and protected health information (PHI) will be kept confidential to the extent possible and as required by HIPAA. All records and data related to the study will be maintained in a secure protected space, with access restricted to study personnel or individuals designated by study personnel who (i) need access to the information to fulfill the terms and obligations of the Coordinating Site or the Sponsor under the Protocol and (ii) are under the same obligations as study personnel to keep the information confidential. It is an open-label study, and each study site will use its own portal only. There are software firewalls in place to prevent site personnel from seeing data from other investigative sites.

Registry Benefits: Subjects will not receive any direct benefit as a result of their participation in the registry. However, information contained within the registry will be used for research studies directed at improving our knowledge and treatment of very early lung cancer diagnosis, screening, and treatment. Identifying best practices for use in small nodule localization may benefit patients with early lung cancer in the future.

8.2 Procedural Data Collection – Risks and Benefits

Procedure-Related Benefits

The Veran ENB SPiN Thoracic Navigation System™ for lung cancer and the SPiN Perc™ Kit (Veran System) were cleared to market by the U.S. Food and Drug Agency (FDA) under 510(k) (K170023). The Veran System is designed to help guide the surgeon with electromagnetic navigation while manipulating small pulmonary nodules. Early detection (and removal) of lung cancer relies upon the precise identification and prompt removal of pulmonary nodules. Deep pulmonary nodules represent a particular technical challenge for surgeons, due to their accessibility. SPiN System biopsy tools are capable of integrating information from imaging devices into real-time visualization, allowing for targeted percutaneous localization of small PPN's. Optimization of this technical localization procedure may result in more accurate identification of small tumors in lung tissue, when used by a skilled, trained surgeon or physician.

Procedure-Related Risks

Reported radiation exposures to the patient from the low dose helical CT procedure are comparable to current practice. No additional procedural risks are anticipated to be introduced.

8.2.1 Anesthesia – Lung Resection Procedure

Sedation and the act of passing a bronchoscope into the airway introduce medical risks. Older adults, or those with serious medical problems, particularly those undergoing more extensive procedures, may be at increased risk of postoperative confusion, pneumonia, or even stroke and heart attack. To mitigate the risks of anesthesia, anesthesiologists or anesthesiology nurses and/or a respiratory therapist typically monitor all patients during the procedure per their institutional protocols and training. In addition, oxygen saturation (using pulse oximetry), respiratory rate, blood pressure, ECG, and heart rate are typically continuously monitored. Patients are not released until they are fully awake and medically stable.

The benefits of anesthesia are that subjects will not feel or remember the pain of the surgical procedure.

8.2.2 Bronchoscopy – Lung Resection Procedure

The greatest risks from bronchoscopy, used as a step to align (“register”) the subject’s day of surgery CT with the subject’s current position on the surgical table, are related to sedation and to the act of passing a bronchoscope into the airway. To mitigate the risks of bronchoscopy, subjects will be under general anesthesia. Subjects are typically monitored during this

procedure. In addition, oxygen saturation (using pulse oximetry), respiratory rate, blood pressure, ECG, and heart rate are continuously monitored. Patients are typically hospitalized following lung surgery for approximately days in the US and released when medically stable.

8.2.3 Trans-thoracic Nodule Localization – Registry Procedure

The risks associated with trans-thoracic nodule localization are bleeding and pneumothorax,

The measures to mitigate the risks are the same for all surgical procedures. Patients are given supplemental oxygen and their oxygen level is continuously monitored using pulse oximetry. A nurse or physician continuously monitor patients' ECG, heart rate, blood pressure, and blood oxygen during the procedure.

9. RESEARCH METHODS AND DATA COLLECTION

In this study, the “lung resection and after care protocol” is determined by each investigator’s current practice, with an outline provided in the registry to explain the context for the type of data collection performed in this patient population. The medical device is being marketed for and used within its intended use.

Localization methods and outcomes, and data related to the nodules, diagnosis, and the setting of the planned clinical intervention of nodule removal will be recorded. Data will be collected according to descriptions below, Table 1 and Figure 1.

Collected data include brief medical history, smoking history, demographic characteristics, radiographic characteristics, procedural characteristics, crossover to other procedures, and adverse events, as follows:

- *Radiographic Characteristics:*

The location of the target nodule (side, lobe and segment, i.e. right upper lobe anterior segment, etc.) will be determined and recorded. The radiographic information collected from CT will include size of the nodule (longest axis), distance from a visible bronchus, and distance from the pleural surface perpendicular to the nodule.

- *Procedural Characteristics:*

Collected procedural information will include the distance of target from pleura nodule statistics (volume, RESIST diameter, maximum, minimum, and effective diameter), and target motion. The duration of the localization procedure will also be recorded.

- *Crossover to Other Procedures:*

All procedures performed to aid in the surgical management of patients – will be noted. Wedge resection, segmentectomy, and lobectomy. The type of initial surgery planned, and the eventual surgery done, will both be collected.

- *Adverse Events:*
All device and/or procedure related adverse events will be recorded for the study localization procedure. Events will be collected from the initiation of the localization procedure to the start of the wedge resection procedure. Study sites will report localization-related adverse events and complications to their IRBs according to institutional requirements. These will be recorded.

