	
The study will enroll between 70 and 100 subjects who fall within current clinical practices to have their PPNs removed at approximately 5 geographically diverse sites across the US. These subjects will undergo intraoperative, EMN-aided percutaneous nodule localization and subsequent resection as part of their normal care. Safety data (adverse and severe adverse events) regarding these subjects will be collected for the localization procedure.
 
All surgical and post-surgical treatment decisions and clinical assessments will be at the discretion of the subject's thoracic surgeon. Eligible subjects from participating sites will be enrolled following identification of a qualifying nodule, and meeting inclusion/exclusion criteria and completing informed consent.
 
Data Collection
 
Registry data will be collected before, during, and after the procedure from the subject's medical records by site personnel. Based on current clinical practice, it is anticipated that subjects will be seen following nodule identification and workup to determine the treatment plan and preparation for surgery (baseline visit). The size and location of the nodule, demographic data and data about smoking history will be collected. Comorbidities will be collected from medical history, and the subject's lung function test results collected.
 
The subject will return to the site for surgery. A non-contrast chest CT scan is recommended within 24 hours/same day as surgery, as a clinically indicated procedural planning tool (Appendix D – Veran CT scan). Otherwise, a non-contrast chest CT scan within the past 15 days is adequate. Subjects are typically given general anesthesia for surgery. The localization technique and material used will be recorded, including volume and type of dye, which needle used, and any other fiducial markers (e.g. microcoil). Localization procedure-related adverse events and device-related adverse events will be recorded. The type and technique of resection performed will be collected (VATS, RATS, thoracotomy, etc.). Subjects recover in hospital and are discharged per standard of care. Any localization-related adverse events will be reported, however the overall lung surgery procedure itself is not being studied (approved indication). Subjects will typically return to the clinic a few times to be seen for scheduled post-operative visits to monitor recovery.
 
A secure, site portal that is 21 CFR part 11 compliant is used for the electronic data entry and reporting at each site, which includes appropriate firewalls between sites and users to protect subject

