STATISTICAL ANALYSIS	
Statistical Considerations
 
This is a registry study where no formal hypothesis is being tested. Data collected during the study will be summarized using descriptive statistics and graphical displays. Generally, demographic and other descriptive characteristics will be described as counts and percentages for categorical variables and as measures of central tendency (mean, median, standard deviation [SD], and range) for continuous variables. Ninety five percent (95%) confidence intervals will be presented for key variables and measures of effect. In some cases, data may be summarized by demographic, response, or treatment subgroups (for example by age, sex, nodule size, smoking history and post-surgical smoking pack years, pulmonary function tests, etc.). No adjustments will be made for multiple comparisons. All localization-related adverse events will be listed and summarized.
 
Interim and Final Analyses
 
Data collected during the study, which is open-label and non-randomized, will be analyzed and reported periodically by an executive steering committee comprised of thoracic surgeons. When the study is completed, a final analysis will be performed and reported.

DATE OF ORIGINAL PROTOCOL	June 11, 2019
DATE OF AMENDMENT	November 2, 2020

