If the nodule is fully removed in crossover cases, then the primary endpoint is met. The nodule may be removed per the surgeon's judgement. The pathology findings will then identify the entire case as either benign or malignant, and the primary endpoint is met.

If Diagnosis is Non-malignant

If the nodule is deemed non-malignant, cells are identifiable, then the positive box for diagnosis is checked, and:

- The nodule must have an intact margin of a cell as a perimeter to be diagnostic.
- The type of nodule (ground glass opacity, etc.) is collected from the pathology report.

The pathology findings will then identify the case as either benign or malignant.

9.3 Safety Objective:

Record Safety Events During Intraoperative Percutaneous Localization Only

To collect and evaluate the safety of nodule localization, including incidence and severity of localization-procedure related adverse events (AEs) and serious adverse events (SAEs) that occur during the localization procedure.

Baseline/Enrollment

All patients will be provided with information about the registry and will sign the informed consent form before any registry-related assessments are made. The following data will be collected at baseline for all enrolled patients:

- To be collected at baseline visit: Review of inclusion/exclusion criteria.

Localization Period

- The localization period begins when the needle touches the subject's skin.
- Localization ends when the localization needle is withdrawn from the subject for the final time.
- Any adverse events that develop during the localization procedure will be reported.
- Bronchoscopy-related events that occur during the alignment of the CT with the patient ("registration") will be recorded.
- Percutaneous localization step, injection of dye, injection of any microcoils, etc.

The process used for AE reporting conforms to Veran Medical Technologies, Inc., standard operating procedures (SOPs) for Medical Device Reporting (MDR)(Appendix C). Training on AE/SAE/MDR reporting practices will be provided to each participating site.

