10.3 Adverse Events – Data Collection for Localization Events

An adverse event (AE) is any untoward medical occurrence, unintended disease or injury, or untoward clinical signs (including abnormal laboratory findings) in subjects, users or other persons, whether or not related to the investigational medical device. Note: Pre-existing conditions are not considered to be adverse events unless there is a change in the nature or severity of the condition.

We will collect data on the localization adverse event through subject discharge from hospital. Principal Investigators were taught to use FDA 3500A MedWatch (Appendix C) and were taught to fill those out during the investigator meeting, for relevant SAEs and also for medical device complaints. This registry's primary safety objective is to collect localization-related safety events in patients undergoing localization prior to wedgeectomy.

The Medical Device Reporting (MDR) regulation (21 CFR 803) contains mandatory requirements for device user facilities (including hospitals, surgical facilities and other) to report certain device-related serious adverse events and product problems to the FDA. These are described in the forms in Appendix C, and the FDA's Guidance for User Facilities.

- User facilities must report a suspected medical device-related death to both the FDA and the manufacturer within 10 days.
- User facilities must also report a medical device-related serious injury to the manufacturer (Veran Medical Technologies, address below).
- In addition, each IRB and institution may have its own policies regarding the content, format, and timing for the reporting of safety information.

¹ The Electronic Code of Federal Regulations (www.ecfr.gov) - <https://www.ecfr.gov/cgi-bin/textidx?SID=244dabc113521b0a851a5db147554fdd&mc=true&node=pt21.1.50&rgn=div5> accessed 4/16/2019.

Each investigator or delegate is responsible for fulfilling these duties.
Please report device serious adverse events to Veran as noted below on form 3500A
(Appendix C).

Please scan and send completed forms to:
Email: [contact]
Email: [contact]

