10.4 Causality – Adverse Event Relationship

The PI will assess the relationship of an adverse event to the device and procedure as follows:

- *Not Related*: No relationship appears to exist between the AE and the device and/or procedure.
- *Related*: The AE follows a plausible temporal sequence following administration of the study device and/or execution of the procedure.
- *Undetermined*: It is not possible to determine the relationship of the AE with the study device and/or procedure.

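### The adverse-event capture and listing rules contradict each other and Undetermined events are not assigned, so the safety incidence is not well defined and could be understated

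*Combined protocol and SAP*

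**What the plan says.** Some places limit the events to related ones:

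- Section 9, Adverse Events: "All device and/or procedure related adverse events will be recorded for the study localization procedure".
- Synopsis, Study Design (Data Collection): "Localization procedure-related adverse events and device-related adverse events will be recorded".
- Synopsis, Safety Assessments: collection is described for localization-related events.
- Synopsis, Statistical Analysis: "All localization-related adverse events will be listed and summarized".

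Other places carry no such limit:

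- Section 9.3 (Safety Objective), Localization Period: "Any adverse events that develop during the localization procedure will be reported".
- Synopsis, Study Design: "Safety data (adverse and severe adverse events) regarding these subjects will be collected for the localization procedure".
- Section 10.3 defines an adverse event "whether or not related to the investigational medical device".
- Section 11.2.1 has SAEs and AEs listed and summarized, with no mention of relatedness.

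Section 10.4 gives the causality call to the PI, with three categories: Not Related, Related and Undetermined. The last is defined as: "It is not possible to determine the relationship of the AE with the study device and/or procedure". The end of section 2 makes it an overarching aim that localization and resection stay with the principal investigator.

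The safety objective in section 9.3 is to evaluate safety, "including incidence and severity of localization-procedure related adverse events (AEs) and serious adverse events (SAEs) that occur during the localization procedure". The Synopsis words its safety objective more narrowly, as the incidence of device-related events during localization.

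**The concern.** The safety objective is an incidence, so it needs a fixed rule for which events enter the database and which of those are counted. The protocol gives two rules for the first and none, as far as Undetermined events go, for the second.

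The order of steps matters. If relatedness decides whether an event is recorded, the causality judgement comes before data capture, and the person making it is the operator. No independent adjudication is described. An event left out at that stage leaves no trace in the registry, so neither the steering committee nor a later analysis could revisit the judgement. Sites that read the wording differently, or draw the line between Related and Undetermined differently, would then report rates that differ for reasons unrelated to safety.

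**Working it through.** The plan states no expected adverse-event rate and no figure that depends on this rule, so there is no number to reproduce. The check is to follow an event in the localization period through each step.

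**1. Capture.** What each rule requires, by the PI's later rating:

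| Rating (section 10.4) | Section 9 and Synopsis Data Collection | Section 9.3 Localization Period |
|---|---|---|
| Related | record | report |
| Undetermined | not required on a literal reading | report |
| Not Related | not required | report |

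The rules agree only on the first row. Strictly, section 9 requires the related events and does not forbid the others, so a site that records everything satisfies both. A site that treats section 9 as the full requirement does not satisfy section 9.3.

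**2. Classification.** Section 10.4 needs events in all three rows. If only related events were captured, Not Related would have nothing to hold. The scale therefore fits section 9.3 and not the literal wording of section 9.

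**3. Listing.** The Synopsis lists localization-related events and section 11.2.1 lists AEs and SAEs. The unfiltered listing does not repair a filtered capture rule, because a listing shows only what was recorded.

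**4. Incidence.** Let N be the evaluable subjects, R those with at least one Related event, and U those with an Undetermined event but no Related one.

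- Related-only incidence = R/N
- Related plus Undetermined incidence = (R + U)/N
- Difference = U/N

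Section 11.1 gives N = 70 to 100, so each subject counted in U moves the rate by 1/100 = 1.0 to 1/70 = 1.4 percentage points. The documents give no value for U. If all events are captured, both rates can be reported. If the Related and Not Related ratings are correct, the true incidence lies between them. If Undetermined events are not captured, only R/N is available and the width of the gap is unknown.

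**5. A purely hypothetical scale.** The one related complication rate in the documents is the pneumothorax count in the pilot study in section 7: 5/24 = 20.8% (stated as 21%). Take p = 5/24 as a true rate and let u be an assumed share of events rated Undetermined and left out. The observed rate is then p × (1 − u):

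- u = 0: 20.8%
- u = 10%: 18.8%
- u = 30%: 14.6%
- u = 50%: 10.4%

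This shows direction only. The pilot was a 24-subject biopsy study, u is invented, and the formula assumes that every omitted event was truly caused by localization.

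**The case against.** A reader might infer three stronger things: that events are recorded only if judged related, that Undetermined events drop out, and that the incidence is therefore biased low. The documents do not support these as facts.

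- Much of the text is unfiltered. Besides sections 9.3, 10.3 and 11.2.1, Table 1 schedules AEs and SAEs at baseline and Day 0 without qualification, and section 10.2 limits collection to the localization procedure, not to causally related events.
- No section excludes Undetermined events. The three categories in section 10.4 suggest that events are recorded first and then rated.
- The term localization-related is not defined. The Synopsis explains that the lung surgery as a whole is not under study, so the term may only separate localization events from resection events.
- Section 10.6 says that pneumothorax and bronchopulmonary hemorrhage will be documented, with no relatedness condition. Section 8.2.3 names bleeding and pneumothorax as the risks of localization.
- The section 9 window closes when wedge resection starts, so events in it precede the resection and are less confounded by it. Section 10.4 also sets a low bar for Related, based on a credible time order. Undetermined may be rare.
- The separate SAP announced in section 11.2.1 and the contents of the appendices cannot be seen here, so whether the eCRF filters on relatedness is unknown.

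All of this stands, and it makes the understatement conditional. It does not remove the conflict. Section 9 is where data collection is set out, and a site could reasonably follow it. In that section the relatedness condition stands beside a separate time window, so it is not merely another way of stating timing. A later SAP can settle how Undetermined is counted, but it cannot recover events that were never entered.

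**Conclusion.** The capture and listing rules conflict, and the place of Undetermined events in the incidence is not specified. The safety incidence is therefore not well defined. If a site follows the section 9 wording and treats Undetermined as not related, some events could go unrecorded for good, and the incidence could be understated if any of them were caused by localization. Nothing is lost if sites record all events and Undetermined is counted, or if no event is rated Undetermined. The size of any understatement cannot be calculated from the documents.

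The conclusion rests on the wording alone. It does not assume that the eCRF filters on relatedness, nor that Undetermined will be a common rating. It is worth correcting because the loss, if it occurred, could not be repaired, while the correction is cheap.

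**What to change.** Align section 9 and the Synopsis (Data Collection, Safety Assessments, Statistical Analysis) with the section 9.3 rule:

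- Record every AE with onset in the collection window regardless of relatedness, and have the PI rate it Related, Undetermined or Not Related after it has been entered.
- List all recorded events, including those rated Not Related.
- State in the SAP that the localization-related incidence is Related plus Undetermined, with Related-only shown beside it.

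The collection window is itself described differently in sections 9, 9.3 and 10.3. That is a separate point, but the corrected wording needs one window to refer to.

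The cost is protocol, SAP and eCRF wording and a few extra AE entries across 70 to 100 subjects. The headline incidence may be slightly higher and may include some events not caused by localization, which is why the Related-only rate should stand beside it. Which of the two leads is a reporting choice in a descriptive registry. Capturing all events keeps both available.
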